3.1 Allocation

We applied stratified random allocation to obtain a more balanced distribution of cluster-level covariates between study arms. First, we divided clusters/CSPS by health districts. Then we stratified clusters into 2 strata using available data on a set of criteria:

- Type of catchment area
- Number of villages covered
- Total population size
- Total number of pregnant women and total number of children <6 months
- Number of ANC admissions and proportion of ANC attended
- Distance between CSPS and district hospital

Then we used Stata to assign unique computer-generated random numbers to each cluster, sort numbers, and allocate each cluster in order to one of two study arms (intervention or control).

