4.4 Statistical methods

Descriptive analyses will be used to describe characteristics of the two groups. Testing of differences between the two groups will be done using a random effects regression, accounting for the clustering of errors within and across health center catchment areas.

The randomized study design allows for the identification of causal effects of the maternal nutrition intervention through comparisons of mean outcomes between the treatment and control groups. Key indicators will include dietary diversity (among pregnant women), IFA consumption, weight gain monitoring, and breastfeeding practices (early initiation and exclusive breastfeeding). Impacts will be assessed using difference-in-difference (DID) estimation. Data management, data cleaning and statistical analyses will be conducted using Stata version 15 (Statacorp, USA).

V. Methods: Monitoring

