### 1.2 Impact evaluation study design

The impact evaluation of A&T's interventions used a cluster-randomized design with repeated cross-sectional surveys at baseline and endline. We applied stratified random allocation to 80 health centers (CSPS, Centre de Santé et de Promotion Social) within four health districts (Boromo, Toma, Dande, and Lena), which were assigned to either the A&T intervention (40 CSPS) or control areas (40 CSPS). The baseline survey was conducted in November-December 2019 and the endline survey was conducted in January-March 2021 in the same 80 CSPS catchment areas, thereby creating panel data at the CSPS level (not at individual level). Program implementation duration was approximately 12 months, with a couple of months of interruption due to the COVID-19 pandemic in March-April 2020.

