### 3.3 Impact estimates

The main analysis of impacts will be performed using intent-to-treat (ITT) specifications, wherein all study participants in the originally assigned program group at baseline are included in the statistical analysis and analyzed according to their program group, regardless of whether they received interventions or not. Women who refused or withdrew consent or those who are ineligible according to study protocol are excluded from ITT analysis.

The main impacts of the interventions will be estimated for: (1) maternal diet during pregnancy, (2) consumption of IFA supplements, and (3) early breastfeeding practices; secondarily, impact will be estimated for exposure to key interventions: (4) maternal nutrition counseling, (5) counseling on IFA supplementation, (6) weight gain monitoring and counseling, (7) breastfeeding counseling. The impact on dietary diversity will be assessed among PW, and impact on all the remaining outcomes will be assessed among RDW.

The difference-in-difference (DID) method will be used to estimate impacts by comparing the changes in outcomes over time (baseline vs. endline) between study arms (intervention vs. control). Point estimates and changes in the outcomes will be reported. For the analysis, the Stata *diff* command will be used, accounting for clustering at the CSPS level with a cluster version of Huber-White robust estimator of standard errors and using degrees of freedom appropriate for the number of CSPS (Hayes & Moulton, 2017). The fixed effects in the two-level regression models will be study arm, survey time, and arm times survey; the latter estimates the difference between arms in changes over surveys. We will conduct ITT analyses based on the original evaluation design, as well as the adjusted ITT analyses using the ITT groups but adjusting for gestational age (for PW only), maternal characteristics, child age and sex (for RDW only), and other variables that may be different between study arms.

Table 6: Dummy table for impact estimates

Indicator	Baseline		Endline		Unadjusted DID	Adjusted DID
	A&T (N=)	Control (N=)	A&T (N=)	Control (N=)		
	Mean (SD)	Mean (SD)	Mean (SD)	Mean (SD)	pp	pp
Dietary diversity score (number of food groups)						
Number of IFA tablets consumed						

	Percent	Percent	Percent	Percent	
Minimum dietary diversity ( $\geq 5$ food groups)					
Consumed 180+ IFA tablets					

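### The DID models name no randomisation strata: a small, conditional loss of precision, and adding strata needs a matching variance correction

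*SAP*

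**What the plan says.** Protocol 3.1 describes the allocation: "First, we divided clusters/CSPS by health districts. Then we stratified clusters into 2 strata using available data on a set of criteria". Random numbers were then used to "sort numbers, and allocate each cluster in order to one of two study arms". SAP 1.2 confirms it ("We applied stratified random allocation to 80 health centers"), in four health districts with 40 CSPS per arm, and says that the same 80 catchment areas were surveyed at baseline and endline.

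On the analysis, SAP 3.3 states: "The fixed effects in the two-level regression models will be study arm, survey time, and arm times survey". Standard errors come from a "cluster version of Huber-White robust estimator of standard errors and using degrees of freedom appropriate for the number of CSPS". The adjusted model adds gestational age, characteristics of the mother, the infant's age and sex, and "other variables that may be different between study arms". Neither model names district or stratum. Protocol 4.4 does not name them either: "Testing of differences between the two groups will be done using a random effects regression".

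**The concern.** An analysis should normally reflect the restrictions used in the randomisation. Stratified allocation balances the arms within strata, so any part of the outcome that the strata predict no longer varies between the arms by chance. A standard error that ignores the strata still counts that part as noise.

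In a DID the question is narrower. The same CSPS appear in both surveys, so stable differences between strata drop out of the change. They do so exactly when each CSPS's relative sample size is the same at both surveys, and approximately otherwise. Only strata that predict the change itself matter. They might do so here, because the stratification criteria include ANC admissions and attendance, population size and distance to the district hospital, and the intervention is delivered through ANC. No passage shows that they do. What is at stake is the width of the confidence intervals, and some power, for the two primary outcomes.

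**Working it through.** **Inputs from the documents (Protocol 2.5, SAP 1.2 and 1.3).** 80 CSPS, 40 per arm. Pregnant women (PW): 480 per arm, so m = 12 per CSPS, ICC 0.110, detectable difference 0.37 food groups. Recently delivered women (RDW): 960 per arm, m = 24, ICC 0.206, detectable difference 15 tablets. Alpha 5%, power 80%.

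**Assumptions, because the documents give no figure.**
- s, the share of survey-specific between-CSPS variance explained by strata: 0-30%.
- CAC, the correlation of a CSPS's effect between surveys: 0.5 and 0.8.
- Layout: eight strata (4 districts x 2) split 5:5 between arms. Others were tried.
- SD: back-solved below.

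**Step 1: the plan's sample sizes.** No SD is given, so the sample sizes cannot be reproduced independently. Setting n = 2(1.96+0.8416)²·SD²·[1+(m-1)ICC]/d², with design effects 1+11×0.110 = 2.21 and 1+23×0.206 = 5.738, gives SD = 1.376 food groups and 48.97 tablets.

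**Step 2: variance of one CSPS's change, in SD².** V = 2·ICC·(1-CAC) + 2(1-ICC)/m. At CAC 0.5:
- PW: 0.110 + 0.148 = 0.258
- RDW: 0.206 + 0.066 = 0.272

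The DID standard error is SD·√(V/20), or 0.156 food groups and 5.71 tablets.

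**Step 3: what strata could remove.** At s = 30%, strata explain 0.3×0.110/0.258 = 13% of V for PW and 0.3×0.206/0.272 = 23% for RDW. The planned standard error is then too large by 1/√(1-0.128) = 1.07 and 1/√(1-0.227) = 1.14.

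**Step 4: simulated power, eight equal strata.** 60,000 runs per cell on CSPS-level changes. Each cell gives power (%) without strata terms, then with strata terms and a valid standard error.

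| CAC | s | PW | RDW |
|---|---|---|---|
| 0.5 | 0% | 65.2 / 64.6 | 74.3 / 73.7 |
| 0.5 | 10% | 65.6 / 66.4 | 74.9 / 76.7 |
| 0.5 | 30% | 66.8 / 70.8 | 77.8 / 84.0 |
| 0.8 | 10% | 78.0 / 78.2 | 94.6 / 95.0 |
| 0.8 | 30% | 78.6 / 79.9 | 95.8 / 97.0 |

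- *Other layouts (CAC 0.5, s = 30%).* Four strata gain 3.3 (PW) and 5.4 (RDW) points. Eight uneven strata gain 3.6 and 6.2.
- *Individual-level regression (8,000 runs per cell, same CAC and s).* With equal cluster sizes, PW goes from 67.1 to 70.7 and RDW from 77.2 to 83.9. With sizes varied by ±40%, PW goes from 62.5 to 67.0 (+4.5) and RDW from 74.0 to 81.7 (+7.7).
- *Larger s.* In a separate simulation at CAC 0.5 with strata explaining half of the between-CSPS change, RDW rises from 79.5 to 91.3 and PW from 67.2 to 75.6.
- *Uninformative strata.* The loss is 0.2-0.8 points.

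**Step 5: type I error of the plan as written.** It is 5.1-5.4% when s = 0. At CAC 0.5 it falls to 4.6% (PW) and 4.4% (RDW) at s = 10%, and to 3.8% and 2.9% at s = 30%.

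**Step 6: which terms, and which variance.** Stratum main effects alone leave the DID estimate unchanged when cluster sizes are equal, so the stratum × survey terms do the work. With them, the 80 changes are in effect fitted with S stratum terms and one arm term, leaving 80-S-1 residual df. The default clustered variance still scales by about 80/79. For S = 8 the standard error is therefore too small by √(71/79) = 0.948, and the type I error on 71 df is about 6.3%. Simulation gives 6.0-6.8% with eight strata and 5.4-5.7% with four. With 80/(80-S-1) as the factor it is 4.9-5.5%.

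**The case against.** The strongest reply is that no harm has been shown. The planned test holds its level, or errs on the conservative side. Whether strata predict change is unknown, and s, CAC, SD and the stratum layout are all assumed. That stands, and it limits this to an optional improvement. The 30% cap on s is also a choice; a higher share would give a larger gain.

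It can also be said that strata are not excluded, because the adjusted list is open and SAP 3.3 ties the ITT analysis to the trial's design. The accurate statement is that strata are not named. The open clause selects on differences between arms, which stratified allocation is meant to remove, so it would not reliably bring strata in. The reference to the design adds no model term.

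Three stronger readings should be resisted.
- A reader might infer that ignoring strata biases the estimate or invalidates the test. It does neither; the direction is conservative.
- A reader might blame the strata for power of about 65% (PW) and 74% (RDW) at CAC 0.5. Those figures appear with s = 0 too. They come from applying a DID variance to SDs back-solved from a single-survey formula, which is a separate matter.
- A reader might think that adding district as a covariate settles it. Main effects alone do almost nothing in a DID.

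**Conclusion.** The point holds as a minor efficiency matter. The strata used in the allocation are named in neither DID model. The result is a standard error that is too wide if the strata predict change, and nothing otherwise. Under assumed s of 10-30% and CAC of 0.5-0.8, adding them changes power by about 0 to +4.5 points for dietary diversity and about 0 to +8 points for IFA tablets. The primary conclusion is not put at risk. The variance correction is the part that most needs care, because adding the terms with the default standard error would turn a test that holds its level, or is conservative, into a mildly anti-conservative one.

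**What to change.** In SAP 3.3, add the randomisation strata as actually used, and their interaction with survey, to the planned individual-level DID regression, both unadjusted and adjusted. Keep the CSPS-clustered robust standard errors, but use G/(G-S-1) as the small-sample variance factor, with G-S-1 df: 80/71 and 71 df if S = 8, or 80/75 and 75 df if S = 4. Compared with the default this widens the standard error by √(79/71) = 1.055 or √(79/75) = 1.026. Cutting only the df is not enough.

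State S and whether the two strata were formed within districts, since the factor depends on it. If Protocol Appendix 1, which was not in the text available, already shows this, a cross-reference will do.

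SAP 1.2 reports the endline survey as completed, so date the change before any comparison of outcomes by arm. If outcomes have already been examined, report the planned model alongside.

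The cost is a few lines of SAP text, a stratum variable that the team should already hold, slightly more work than the default *diff* command, and S-1 df. If the strata prove uninformative, under 1 point of power is lost.

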### 3.4 Plausibility analysis

In addition to the estimation of impacts, we will conduct plausibility analyses by two methods, to provide further evidence for the likelihood or strength of our impact estimates. First, we will assess whether social desirability bias may have influenced reported outcomes. Second, we will examine the intermediate outcome indicators along the program impact pathways (from service delivery to exposure and behavioral determinants) to determine whether the program resulted to the outcomes as intended by design.

#### 3.4.1 Testing for social desirability bias

For outcome measures based on individual report, social desirability bias may play a potential role in influencing response. We applied a 13-item social desirability index, adapted from Reynolds and Gerbasi (Reynolds, 1982), to determine the extent to which respondents were likely to report behaviors based on their desire to please others, present oneself to others in a favorable way, or for social approval, i.e., “social desirability”:

No.	Question item	
1	Is it sometimes hard for you to go on with your work if you are not encouraged?	NOO=1
2	Do you sometimes feel resentful when you don't get your way?	NO=1
3	Do you occasionally give up doing something because you don't think you have the ability?	NO=1
4	Do you occasionally feel like not listening to people even though you know they were right?	NO=1
5	No matter who you're talking to, are you always a good listener?	YES=1
6	Have there been occasions when you took advantage of someone?	NO=1
7	Are you always willing to admit it when you make a mistake?	YES=1
8	Do you sometimes try to get even, rather than forgive and forget?	NO=1
9	Are you always courteous, even to people who are disagreeable?	YES=1
10	Have you ever been irritated when people expressed ideas very different from your own?	NO=1
11	Have there been times when you were jealous of the good fortune of others?	NO=1
12	Are you sometimes irritated by people who ask favors of you?	NO=1
13	Have you ever deliberately said something that hurt someone's feelings?	NO=1
	Total score	13

The social desirability score (SDS) will be created by adding up the number of socially desirable answers, out of the total 13 question items. We will conduct three analyses using this score: (1) estimation of mean SDS by program group to compare differences in the level of social desirability bias between the intervention and control groups; (2) tabulation of key outcomes by SDS to assess whether the reported outcomes varied by SDS levels; and (3) regressions with each of the outcomes as dependent variables to test the interaction between SDS and intervention group, to determine whether or not social desirability bias differentially affected the impact of the A&T interventions on key outcomes.

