2.5 Sample size

The two main samples for the primary outcomes are: 1) pregnant women (PW) as this sample allows the assessment of diet quality during pregnancy; and 2) recently delivered women (RDW) who have children under 6 months of age, as this sample provides the best opportunity to assess the primary outcome related to intervention exposure throughout pregnancy (i.e., IFA consumption). Based on an initial mean dietary diversity score of 3.52 food groups across both regions and intra-cluster correlation of 0.110 from the 2019 baseline data (Kim et al., 2020), a significance level of 5% and power of 80%, the sample size of 480 PW per arm is estimated to detect a difference of 0.37 in the mean dietary diversity score after intervention.

For RDW, using an initial mean of 108.64 IFA tablets consumed across both regions and intra-cluster correction of 0.206 at baseline (Kim et al., 2020) and the same assumptions above for statistical significance, the sample size of 960 RDW per arm is estimated to detect a difference of 15 tablets in the mean IFA tablets consumed after intervention. If husbands of RDW are present at the time of the survey, they will also be interviewed briefly about their health and nutrition knowledge and any support provided during pregnancy. Approximately half of the expected sample size of husbands was available at baseline.

Outside of these two main samples, nurses-midwives (1 per CSPA) and community health workers (within 3 villages per CSPA) will be interviewed. In addition, direct observations of ANC visits (2 per CSPA) to assess service quality, followed by exit interviews to assess client satisfaction, will be conducted among a subgroup of pregnant women attending ANC at the time of survey.

The overall study samples sizes are presented in **Table 2**.

Table 2: Estimated sample sizes

	Baseline 2019		Endline 2020	
	Intervention	Control	Intervention	Control
Pregnant women	480	480	480	480
Women with children 0-5 months old	960	960	960	960
Husbands of women with children 0-5 months old	960	960	960	960
Nurses-midwives	40	40	40	40
Community health worker (ASBCs)	120	120	120	120
ANC observation & exit interview	80	80	80	80
Total	2,640	2,640	2,640	2,640

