### III. Statistical Analysis Plan

#### 3.1 General principles and methods

Data analyses will be performed using STATA version 16.0 (StataCorp LLC). All applicable statistical tests will be two-sided to allow potential findings of unexpected effects. Statistical significance will be presented at levels of  $p<0.05$ ,  $p<0.01$ , and  $p<0.001$ .

A diagram presenting the flow of clusters and individuals through the trial, based on the Consolidation Standard of Reporting Trials (CONSORT) statement: extension to cluster randomized trials (Campbell et al., 2012; Eldridge et al., 2016), is shown as follows.

[figure not shown]

Figure 1. CONSORT flow diagram for repeated cross-sectional surveys

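### A non-significant SDS-by-arm interaction in SAP 3.4.1 (3) cannot support a finding of no social desirability bias; report the estimate with its interval instead of a yes/no decision

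*SAP*

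**What the plan says.** SAP 3.4 introduces the plausibility analyses with "First, we will assess whether social desirability bias may have influenced reported outcomes". SAP 3.4.1 then defines a 13-item score and three uses of it: (1) mean score by program group, (2) key outcomes tabulated by score, and (3) regressions testing the score-by-group interaction. Only the third carries a yes/no purpose: "to determine whether or not social desirability bias differentially affected the impact of the A&T interventions on key outcomes".

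SAP 3.1 adds "Statistical significance will be presented at levels of" 0.05, 0.01 and 0.001, with two-sided tests. Neither section gives an interval for the interaction, an impact at low SDS, an amount of bias that would matter, or a rule for a null result. SAP 3.4.1 also does not name the model, or say whether it uses endline data, both surveys pooled, or a term with survey time. The impact analysis itself (SAP 3.3) is a DID.

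**The concern.** Both primary outcomes are women's own reports, and the protocol (3.2) describes an unblinded trial of intensified counselling on the behaviours being reported. A woman counselled on diet or IFA may over-report them. The SDS analyses are the part of the plan aimed at that risk.

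A test can only settle the question in both directions if it would probably detect a bias that matters. The samples were sized for main effects, not for an interaction. If power is low, a non-significant result is what one would expect with or without material bias, and reading it as an answer would lend the impact estimates support that the data do not give. Uses (1) and (2) do not fill the gap. Randomised arms can have equal mean SDS while counselled women over-report more, and a tabulation does not estimate how much of the impact is bias.

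**Working it through.** **Inputs from the documents.** Protocol 2.5: "the sample size of 480 PW per arm is estimated to detect a difference of 0.37 in the mean dietary diversity score"; "intra-cluster correlation of 0.110 from the 2019 baseline data"; "the sample size of 960 RDW per arm is estimated to detect a difference of 15 tablets", with an ICC of 0.206; 5% significance and 80% power. SAP 1.2: 40 + 40 health centres, hence 480/40 = 12 pregnant women (PW) and 960/40 = 24 recently delivered women (RDW) per centre.

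**Inputs assumed.** The SDS mean and SD are not given. I used 8 (2.5), with a range from 9 (2) to 7 (3), i.e. a coefficient of variation (CV) of roughly 0.2 to 0.4. Over-reporting occurs in the intervention arm only and is proportional to SDS.

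**Step 1: outcome SDs.** These are not stated either, so the plan's sample sizes cannot be reproduced independently. Solving MDE = 2.80 × SD × √(2 × DEFF / n), where MDE is the stated target difference:
- PW: DEFF = 1 + 11 × 0.110 = 2.21; SD = 0.37 / (2.80 × √(2 × 2.21 / 480)) = 1.38 food groups.
- RDW: DEFF = 1 + 23 × 0.206 = 5.738; SD = 15 / (2.80 × √(2 × 5.738 / 960)) = 49 tablets.

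**Step 2: what the interaction sees.** If the whole target effect d is bias proportional to SDS, the interaction slope per SD of SDS is only d × CV. Its endline standard error is SD × √(1 − ICC) × √(2/n):
- PW: 1.376 × √0.890 × √(2/480) = 0.0838. At CV 0.3 the slope is 0.111; 0.111 / 0.0838 = 1.32, so power = Φ(1.32 − 1.96) = 26%.
- RDW: 48.97 × √0.794 × √(2/960) = 1.992. At CV 0.3 the slope is 4.5; 4.5 / 1.992 = 2.26, so power = Φ(2.26 − 1.96) = 62%.

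At CV 0.2 / 0.3 / 0.4 this gives 14% / 26% / 42% for diet and 33% / 62% / 85% for IFA. If half the effect is bias, CV 0.3 gives 10% and 20%.

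**Step 3: simulation.** 80 centres, endline only, SDS rounded and clipped to 0-13, centre-robust standard errors or a random-intercept fit. Base case 8 (2.5), with the range over 9 (2) to 7 (3):

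| Share of target effect that is bias | Power, diet | Power, IFA |
|---|---|---|
| All | about 22-26% (15-43%) | about 47-62% (29-87%) |
| Half | about 10% (6-18%) | 16-19% (10-32%) |

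For IFA the choice of model matters: about 47% with OLS and robust standard errors, about 62% with a random intercept.

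**Step 4: matching the DID.** With SDS × arm × survey, √(2/n) becomes √(4/n). At CV 0.2 / 0.3 / 0.4, power for a 100% bias falls to 10% / 16% / 24% (diet) and 19% / 36% / 57% (IFA). A two-way term pooled over both surveys does no better, because bias present only at endline is diluted by half.

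**Step 5: sensitivity.**
- If all the bias sits in the higher-SDS half of women: 70-99% for diet, about 99% or more for IFA.
- If bias is unrelated to SDS: 5% for both.
- If the sample sizes were set for the DID, the SDs are smaller by √2 (0.97 and 34.6). At CV 0.3, endline power is then 47% and 89%; with the three-way term it is 26% and 62%.
- SDS reliability of 0.6-0.8 lowers endline power at CV 0.3 to 18-22% and 42-52%.

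**The case against.** A reader might infer that the test would usually miss bias in both primary outcomes. The documents do not support that. For IFA the central result runs from about even to better than even, and it depends on a model that SAP 3.4.1 does not name: SAP 3.3 cites robust standard errors and two-level models, while protocol 4.4 and SAP 3.4.2 refer to random- or mixed-effects models. The figures also need an SDS distribution, outcome SDs and a shape of bias that the documents do not give, and bias confined to high-SDS women would be caught readily. This stands, and it limits the size of the claim.

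A reader might also infer that the plan will take p > 0.05 as proof that the impacts are real. It does not say so. SAP 3.1 only says that significance will be presented at three levels; the interaction is one of three SDS analyses in a plausibility section that also contains the impact-pathway work; and the DID inference in SAP 3.3 does not depend on it. This stands too, and makes the point minor.

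Neither argument rescues the yes/no wording. If power can lie anywhere from 5% to 99% depending on unstated quantities, a bare p-value above 0.05 cannot be interpreted. An interval at least shows which interaction sizes the data exclude. It would not reveal bias unrelated to SDS, which is a limit of the instrument under either form of reporting.

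**Conclusion.** The point holds in limited form. SAP 3.4.1 (3) frames a significance test as settling whether bias differentially affected the impact, and a null result cannot settle it. For dietary diversity, with SDs calibrated to an endline comparison and bias proportional to SDS, the test would miss a bias equal to the whole 0.37 food groups roughly three times in four. For IFA it would miss a bias equal to the whole 15 tablets in about 38-53% of cases (100% minus 62% and 47%). If half the effect were bias, it would be missed more than 80% of the time for either outcome in the base case. All of this rests on the assumed SDS distribution, the back-solved SDs and the assumed shape of bias. The primary impact analysis is unaffected; this is a cheap improvement to a supportive analysis.

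**What to change.** In SAP 3.4.1 (3), for each primary outcome:
- Replace the yes/no determination with the interaction estimate and its 95% CI.
- Report the impact with its 95% CI predicted at a low SDS (for example the 10th percentile) and at the mean SDS.
- Name the model, and use surveys and a time term that match the DID impact model.
- State that a non-significant interaction is not evidence of no bias, and report the check as inconclusive when the interval is compatible with bias as large as the estimated impact.

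A numerical pass mark, such as bias below a fixed share of the impact, is not needed: the share would be arbitrary, and computing it as slope times mean SDS extrapolates to a score of zero.

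The cost is a few sentences and one post-estimation step on data the surveys already collect. The downside is that the check will often be reported as inconclusive, all the more because the DID-matched term is less precise than an endline-only one.
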